5.2 Treatment assignment

We designed a two-stage randomization process to study both direct treatment and spillover effects of health insurance.

In a first stage, we randomly assigned villages to one of five village-level arms. A village-level arm is defined by the percentage of households within the village assigned to each of the four household-level study arms defined in subsection 4.2.1. The percentage allocations to the 4 household-level arms are given in the last 4 columns of Table 1. The percent of villages assigned to each of the 5 village-level arms are in the second column. Villages were matched before this first stage randomization.⁷

Table 1: IHIE Two-Stage Randomization Design

Village-level arms (%)		Household-level arms (%)			
Arm	Village allocation	Group A	Group B	Group C	Group D
I	15	30	50	10	10
II	15	30	10	50	10
III	15	30	10	10	50
IV	35	70	10	10	10
V	20	10	30	30	30
Total	100	40	20	20	20

In a second stage, we randomly assigned households within a village to the four arms according to the allocation probabilities assigned to the village. Households were matched before this second stage randomization.⁸

The target enrollment for each of the 4 household-level arms, unconditional on village-level arm, was 4,500 households for condition A and 2,250 households for each of conditions B, C and D. Due to some attrition between listing and completion of baseline, our final randomized sample amounted to 11,089 households in 424 villages in the two districts.

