5.4 Treatment Delivery

The population that is eligible for this study would not be eligible for RSBY under the program's usual rules. To make this study possible, we exchanged letters of cooperation with the state in which we conducted the study (Karnataka), the central government agency (Ministry of Labor) responsible for administration of RSBY, and the development organization (GIZ) providing technical support for RSBY.

Sample households were randomized in August 2014 using data from the listing exercise. They were informed of their treatment assignment and, depending on which arm to which they are assigned, given access to insurance or cash in May and June 2015. This step took place roughly 18 months after the baseline due to government constraints. Due to challenges associated with evaluating a government program, we were only able to enroll sample households when the government held its RSBY enrollment drive in early 2015.

We enrolled study households much in the same way the government enrolled RSBY (non-study) eligible households into the program: via a mobile enrollment truck that visited each village. One difference is that we went to each household to ask them if they would like to enroll and took them to the enrollment truck, which was parked in one place in the village. By contrast, the government informed non-study households by delivering paper notices (chits) to each home about when and where the enrollment truck would be in the village.

Roughly 78.4%, 70.4% and 58.6% of households in arms A, B, and C, respectively enrolled in RSBY. Enrollment rates are somewhat higher in Gulbarga than Mysore: 77.9/76.4/64.1% v. 78.8/63.5/52.3% in A/B/C. No one in arm D enrolled.

For all study households that take up insurance, we paid the government their premiums. For households in arms A, this was funded by grant funds. For those in B and C that purchase insurance, this was funded by the respondents' money.

The Karnataka government renewed RSBY automatically for non-study and study households in 2016 and 2017 without any action—even payment—by enrollees. RSBY ended in the state on August 31, 2018, to make way for the new NHPS scheme, which is scheduled to start in late 2018 or early 2019. As of this writing, Karnataka had agreed to roll out NHPS but had not begun the roll-out.

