7.2 Complier average treatment effect (CATE)

Our second parameter of interest is the CATE estimate for the impact from uptake of insurance. Our basic regression model to estimate this has a two-stage least squares structure:

$$y_{ijt} = \alpha + \theta s_j + \phi z_{ij} + \rho s_j z_{ij} + \psi X_{ij} + u_{ijt} \quad (3)$$

where z_{ij} is the binary enrollment variable by household i in village j , and $s_j = \sum_{i=1}^{n_j} z_{ij}/n_j$ is the enrollment rate in village j . We estimate this equation using instrumental variables, d_j^v , d_{ij}^h , and $d_j^v d_{ij}^h$ (see Appendix E.2 of [name], Jiang, and [name] (2019), for $(s_j, z_{ij}, s_j z_{ij})$). The remaining variables are defined as in equation (2). In particular, the control variables and weighting are managed as they are in the previous section.

Identification. The exclusion restriction for CATE estimation is that treatment assignment only affects household outcomes through the decision to enroll in RSBY (see [name], Jiang, and [name] (2019) for details). Note we are not instrumenting *utilization* of RSBY, which would require a stronger exclusion restriction. We are instrumenting enrollment in RSBY.

Spillovers. To address the possibility of spillovers, we do many of the things we do for the ITT analysis. For example, as discussed by [name], Jiang, and [name] (2019), we will use the cluster robust HC2 variance or the weighted average of individual and cluster robust HC2 variances. The most important difference is the assumptions required for unbiased estimation with spillovers, as given in [name], Jiang, and [name] (2019). Beyond partial non-interference as before, we must assume that for noncompliers their treatment assignment does not affect their outcome through the enrollment of other units. Moreover, we test for the existence of spillovers by testing the null hypothesis that $\theta = 0$ and $\rho = 0$.

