8.5 General coloring variables

The following is a non-exhaustive list of variables that may be used as control variables that measure dosage, specific margins of response or dosage. This list is non-exhaustive as it lists only those variables measured at endline and not otherwise included as a coloring variable above.

- Gender of respondent
- Age of respondent
- Role of respondent in household (relationship to head of household)
- Size of household
- Number of adults in household
- Number of children in household
- Knowledge of BPL households and how many
- Knowledge of BPL households with RSBY cards and how many
- Knowledge of household that successfully used RSBY
- Knowledge about RSBY (number correct out of 4 questions)
- Knowledge of when RSBY scheme expired
- Subjective willingness-to-pay for RSBY
- Knowledge about NHPS
- Does respondent think household is covered by NHPS
- One item test of NHPS (does respondent know about amount of coverage)
- Did any other individuals assist with answering questions during the survey? If so, what is the gender and relationship to respondent? ¹⁷

¹⁷Additional respondents may affect the response quality in both positive and negative ways. For finance questions, these individuals may improve the precision of the responses. For health questions, these individuals may lead to decreased precision. Please note that enumerators were instructed to administer health questions without any additional individuals present to minimize this concern.

9 Structural modeling

We plan to develop an economic model of household financial decisions and health status. We will structurally estimate the model using the experimental variation, to quantitatively reconcile the rich set of empirical results and perform counterfactual analysis.

10 Why is higher price for insurance associated with higher utilization?

At midline we found that individuals in group C, which had to pay a premium for insurance but did not get an unconditional cash transfer, had higher rates of utilization of the RSBY card. We will explore three explanations. First, individuals that value insurance more because they are more likely to use it are more likely to take up insurance, i.e., there is selection. Second, a higher price for a good sends a positive signal about the quality of the good, and higher quality goods are consumed more. Third, there is some sunk cost effect.

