10.3 Price signaling

We test this explanation by testing its prediction that, assuming individuals learn about prices not just from their own experience but also from the experience of their peers, individuals who live in villages where there are more people who received insurance at a lower price (e.g., zero) should perceive insurance as having less value and thus purchase it less themselves. We test this prediction by examining the following:

- Holding constant the group assignment of a household, the household should attempt to or utilize care more the higher is price paid by other households that are both in the study sample and in the same village.

¹⁸The price of RSBY is fixed under our study—and for BPL families in the actual scheme—regardless of the size of the household.

¹⁹By contrast, average utilization could be lower in A than C if you only look at enrollees, i.e., the CATE estimates for A could be lower than for C even if there is selection.

- Holding constant the group assignment of a household, the household should attempt to or utilize care more the higher the price paid by other households that are in the same village, including both other households in the village and the fraction of households in the village that are below the poverty line.

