11.1 Estimation

We examine both the existence of spillovers and the mechanisms behind those spillovers. Our source of variation is the village-level group to which a household is indirectly allocated via the first stage of randomization. These analyses will take the form of examining whether outcomes (e.g., utilization, consumption, assets, health) and intermediating variables (e.g., incidence of gifts and loans, knowledge of RSBY, asset prices) within a given treatment assignment (groups A–D) differ according to the stratum to which the village was assigned.

We will estimate spillovers directly from our ITT and CATE analyses. Because both positive and negative spillovers are possible, we will use two-sided tests. We weight villages equally as that is the level at which we posit that spillovers occur.

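### For RSBY card use, the CATE spillover test in 7.2 over-rejects if use per enrollee differs between arms A, B and C

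*Combined protocol and SAP*

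**What the plan says.** Section 7.2 models the outcome on village enrolment s_j (coefficient theta), own enrolment z_ij (phi) and their product (rho). Here z_ij "is the binary enrollment variable by household", with one coefficient whatever the arm. On estimation it says "We estimate this equation using instrumental variables", namely the village-group indicators, the household-arm indicators and their products. For spillovers, "we test for the existence of spillovers by testing the null hypothesis that" theta = 0 and rho = 0. Section 11.1 draws spillover estimates from both the ITT and the CATE analyses, adding: "Because both positive and negative spillovers are possible, we will use two-sided tests".

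Two other places bear on the single phi. The opening of Section 10 reports that at midline group C "had higher rates of utilization of the RSBY card". Footnote 19, attached to 10.2, says that "the CATE estimates for A could be lower than for C even if there is selection".

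**The concern.** The null that equation (3) actually generates is a joint one: no spillovers, and the same enrolment effect in A, B and C. The second part may well fail for card use, because those who pay and those who enrol free can be different people. Table 1 changes the mix of arms from one village group to another, so village enrolment moves together with that mix. A difference between arms can then load on theta and rho although no household affects another.

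At stake is the reading of a rejection for outcomes such as trying to use the card or managing to use it. It could be taken as evidence that insured neighbours change a household's behaviour (evaluation question 3) when it reflects only how households obtained cover (question 2). The false pattern has a plausible look: enrollees appear to use the card less where village enrolment is highest, which is group IV, where 70% of households are in the free arm. That resembles the peer-price prediction in 10.3.

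**Working it through.** **Inputs from the plan.** Table 1: village groups I-V hold 15/15/15/35/20% of villages, with A/B/C/D shares of 30/50/10/10, 30/10/50/10, 30/10/10/50, 70/10/10/10 and 10/30/30/30. Section 5.4: "Roughly 78.4%, 70.4% and 58.6% of households in arms A, B, and C, respectively enrolled in RSBY"; none enrolled in D. Section 5.2: 11,089 households in 424 villages. Section 7.1: equal village weights for spillovers and village-clustered HC2 standard errors.

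**Assumptions not in the plan.** A 5% level, the card-use rates per enrollee, the spread of village sizes and endline retention (one simulation used the midline figure, 10,111/11,089 = 91.2%).

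**Step 1: reproduce the plan's figure.** Arm A: 0.15×30 + 0.15×30 + 0.15×30 + 0.35×70 + 0.20×10 = 40%. The other arms give 20% each, matching the Total row of Table 1. The plan states no size or power for the CATE spillover test.

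**Step 2: expected village enrolment**, s_v = sum over arms of share × enrolment rate.
- I: 0.3×0.784 + 0.5×0.704 + 0.1×0.586 = 0.646
- II: 0.599
- III: 0.364
- IV: 0.7×0.784 + 0.1×0.704 + 0.1×0.586 = 0.678
- V: 0.465

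**Step 3: why a single phi fails.** With no spillover, mean card use in arm h is phi_h × p_h in every village group, where p_h is the arm's enrolment rate. At 10/12/16% use per enrollee this is 0.10×0.784 = 0.078 in A, 0.12×0.704 = 0.084 in B, 0.16×0.586 = 0.094 in C, and 0 in D. These points do not lie on a line through zero in p_h. The best-fitting line depends on which arms dominate the village group, and that changes with s_v.

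**Step 4: large-sample limit of equation (3), zero spillover.** The 20 cell means are regressed on 1, s_v, p_h and s_v×p_h with cell-share weights.

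| Use per enrollee A/B/C | theta | rho |
|---|---|---|
| 10/10/10% | 0 | 0 |
| 10/12.5/15% | +0.030 | -0.082 |
| 10/12/16% | +0.035 | -0.091 |

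In simulated finite villages the 10/12/16% values are smaller, about +0.02 and -0.06. Over the range of s_v (0.678 - 0.364 = 0.314), the false change for an enrollee is (0.035 - 0.091)×0.314 = -1.8 points in the limit and (0.02 - 0.06)×0.314 = -1.3 points in simulation.

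**Step 5: false rejection of theta = rho = 0 at nominal 5%.** Two-stage least squares with the 20 cells as instruments, village-clustered variance, equal village weights and no spillover in the data. Ranges cover separate simulations with somewhat different village-level assumptions.

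| Use per enrollee A/B/C | Single phi |
|---|---|
| equal in all arms (10% or 12%) | 4-6% |
| 10/11.1/13.4% | 14-18% |
| 20/22.3/26.8% | 34-40% |
| 10/12/16% | about 35-45% |

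The 10/11.1/13.4% row is the case of equal use per assigned household: 10×0.784/0.704 = 11.1 and 10×0.784/0.586 = 13.4. If the midline finding is per assigned household, C exceeds A only when the per-enrollee ratio is above 0.784/0.586 = 1.34. With households weighted equally, the 10/11.1/13.4% row becomes 23-27% and the 10/12/16% row 59%. A cruder run without the HC2 correction gave 29% for 10/11.1/13.4%; it is not relied on, because the plan specifies HC2.

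**Step 6: a general outcome.** For hospital visits (15% base, enrolment adding 3/4.5/6 points in A/B/C), rejection was 4.5-6.9%.

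**Step 7: arm-specific enrolment effects, same instruments.** The model is identified (rank 6 of 6). In the large-sample limit theta and rho return exactly to zero for the unequal-use cases above. Simulated rejection was between 4% and 8%.

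**The case against.** The plan already contains sound spillover tests. The ITT Wald test in 7.1 compares village groups within household arm and can be run on any outcome. Section 11.1 also compares outcomes across village groups within each assignment. Neither needs equal enrolment effects. Section 10.1 compares card use by arm directly, and 10.3 holds a household's own assignment fixed, so the price analyses do not rest on theta or rho. All of this stands. A reader might infer that the plan cannot separate spillovers from price effects, or has no valid spillover test; the documents do not support that. What remains is that 11.1 also draws on the CATE analyses and does not say which result governs if they disagree.

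Second, the use rates are invented. Section 10 gives a direction at midline, with no level, no gap and no statement of whether the rate is per enrollee or per household. Section 10.1 treats persistence to endline as an open question. This also stands: the mechanism is certain, the magnitude is not.

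Third, 7.2 states an exclusion restriction under which assignment acts only through enrolment. That would rule out signalling and sunk-cost differences between arms. It does not rule out selection, which alone makes free and paying enrollees respond differently.

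Fourth, footnote 19 speaks of separate CATE estimates for A and C, so arm-specific effects are contemplated. But 7.2 writes out no model that could produce them or use them in the spillover test.

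**Conclusion.** The point holds in a limited form. The single-phi test of theta = rho = 0 is a test of no spillovers only when enrolment has the same effect in all three arms. For RSBY card use, where the plan itself expects that this may fail, the test can reject at roughly three times its nominal rate (14-18%) for a modest gap between arms, and at seven to nine times (35-45%) for 10/12/16%. These figures rest on assumed use rates and a 5% level.

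A reader might go further and conclude that the plan will report spillovers where none exist. That does not follow: the test is correctly sized if use per enrollee is equal, and in the cases tabulated under the plan's equal village weights it still rejects less than half the time. Nor does the problem extend materially to general utilization, finance and health outcomes, where the excess is small. It concerns essentially the RSBY-use outcomes, and it matters because no rule says which spillover test governs. The change is worth making before the endline analysis.

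**What to change.** In 7.2, for RSBY-use outcomes, replace phi×z_ij with phi_A, phi_B and phi_C times z_ij by arm. Keep theta×s_j, rho×s_j×z_ij and the same instruments, and test theta = rho = 0 in that model. State in 7.2 and 11.1 that the existence of spillovers is decided by this version or by the within-arm ITT test in 7.1, naming which, and that the single-phi version is not used for that purpose.

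The cost is a sentence or two of text and two extra endogenous regressors; no new data are needed. Against a real spillover, simulated power fell by about 1 point: 69% against 70% with equal village weights and 81% against 82% with equal household weights, with 87% against 88% in a separate simulation.

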7.3 Testing for heterogeneous effects

We will examine whether the impact of access to insurance and uptake into insurance varies with certain individual, household and village characteristics at baseline and enrollment. We will estimate these heterogeneous treatment effects as follows. We will interact the characteristics with household and village group indicators. For example, for ITT estimates and heterogeneous impacts from household-level treatments, the estimated equation would be:

$$\begin{aligned} y_{ijt} = & \alpha + \sum_{v=1}^3 \beta_v \sigma_j^v + \sum_{h=1}^3 \gamma_h d_{ij}^h + \sum_{h=1}^3 \sum_{v=1}^3 \lambda_{hv} \sigma_j^v d_{ij}^h \\ & + \sum_{v=1}^3 \beta_{vw} \sigma_j^v w_{ij} + \sum_{h=1}^3 \gamma_{hw} d_{ij}^h w_{ij} + \gamma_w w_{ij} + \sum_{h=1}^3 \sum_{v=1}^3 \lambda_{hvw} \sigma_j^v d_{ij}^h w_{ij} \\ & + \phi w_{ij} + \delta X_{ij} + e_{ijt} \end{aligned} \quad (4)$$

where w_{ij} is the continuous or binary characteristic along which we want to test heterogeneous impacts. The test for heterogeneous treatment effects along w_{ij} is whether we can reject $(\beta_{vw} = \beta_v, \gamma_{hw} = \gamma_h, \lambda_{hvw} = \lambda_{hv}) \forall (h, v)$. In order to ease interpretation, we will make modifications to the above specification analogous to the ones we make to ease interpretation of the ITT regressions.

We will test for heterogeneous treatment effects in two steps. First, we will test for heterogeneity along several basic dimensions¹³ we think are the most likely to generate heterogeneous effects:

1. District
2. Size of household
3. Age
4. Wealth (measured by assets)
5. Number of hospitals nearby or distance to closest hospital
6. Hospital utilization in prior year (measured at baseline)

¹³As noted above, for time-varying characteristics we will use the baseline values.

7. Monthly expenditure budget (measured at baseline)
8. Predicted propensity to utilize inpatient healthcare (described below)
9. Village size
10. Urban status

Second, we will use machine learning methods to help predict which dimensions of heterogeneity (from the list below) are most important (Duflo 2018, [Wager and Athey \(2018\)](#)).

1. District
2. Size of household
3. Cast or religion
4. Number of adults in household
5. Number of kids in household
6. Having children
7. Distance from closest public and/or private hospital
8. Number of public and/or private hospitals nearby
9. Presence or number of private hospitals nearby
10. Gender of subject
11. Age or child/adult status
12. Marital status, birth order and relationship to household head
13. Size of village
14. Percent of village assigned to access to RSBY via this RCT
15. Percent of village eligible for RSBY outside the RCT
16. Hospital utilization in prior year (measured at baseline) or predicted hospitalization
17. Health status or serious sickness
18. Cognitive capacity
19. Willingness to pay for insurance (predicted based on data from a randomly selected sample of households removed from main RCT and chosen to participate in a WTP study)
20. Risk and time preferences
21. Assets and savings
22. Urban, peri-urban, and rural status
23. Monthly expenditure budget
24. Experiencing a serious health shock in the past year (provided this is balanced across treatment arms)

Predicting utilization. A natural dimension along which the impact of insurance may differ is the latent propensity of a household to experience health shocks which would require inpatient care. Since this variable is latent, it must be estimated. We will machine learning methods to predict households' likelihood to experience an inpatient hospitalization. We will perform this exercise on two samples: the baseline data (across all treatment arms) and the post-intervention data (using only group D, the control group). The resulting model will then be used to generate predictions for the full sample. Our key hypotheses are (1) that the impact of the offer of insurance will lead to larger treatment effects for those with higher propensity; and (2) that demand for insurance will be less price-elastic among those with higher propensity (i.e., adverse selection). Hypothesis (2) will be tested by examining how takeup of insurance varies between free and not free (group A vs. groups B and C) for high- vs. low-propensity households.

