In addition, we will estimate two substantively different specifications to abstract away from methods of access to insurance and towards the mere fact of access to insurance. On one, we replace the four household group indicators with an indicator for whether the household was in group A, B or C and we replace the four village-level arm share variables with the share in groups A, B or C.¹¹ Additionally, we will estimate a specification where σ_j^v is replaced by the total share of the village eligible for RSBY, including both the share assigned to A, B and C as well as the share of the village with BPL cards or in certain eligible occupational classifications (who were therefore RSBY eligible).

Control variables. We first estimate a variant of the regression model above without any controls X_{ijs} , where s indicates a time that may not be equal to t . We then estimate a specification where X_{ijs} is a vector of baseline controls (i.e., X_{ijs} at time $s = 0$). We will use machine learning methods to select these control variables. Finally, we will run specifications where X_{ijs} may include so-called “coloring variables” that shed light on mechanisms of impact, welfare effects, and the dosage of treatment. In the latter case, we will include interactions of treatment variables with coloring variables, the same manner in which we estimate heterogeneous treatment effects. These coloring variables are listed in section 8.

Weighting. This regression can be weighted in multiple ways. We could either weight each household equally or weight each village arm identically. When examining household-level access We choose to weight each household equally because no household is obviously more informative than any other, especially when examining questions about the impact of insurance on households. When examining spillovers, we will weight villages equally.

Standard errors. We use the cluster robust HC2 standard errors at the village level. [name], Jiang, and [name] (2019) shows that this is a conservative variance in two-stage randomized experiments.

Spillovers. To address the possibility of spillovers from, e.g., giving some households access to insurance in one way affects households not given access to insurance in that way, we do a few things.

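### The heterogeneity test in Section 7.3 sets each interaction equal to its main effect instead of zero, so it tends to reject a constant non-zero effect and to pass one that doubles

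*Combined protocol and SAP*

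**What the plan says.** The aim of Section 7.3 is clear: "We will examine whether the impact of access to insurance and uptake into insurance varies with certain individual, household and village characteristics". Equation (4) is given as the example for ITT estimates. It contains:

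- main terms for village shares (β_v), household arms (γ_h) and their products (λ_hv), none of them multiplied by w or by 1 − w;
- the same terms multiplied by w, with coefficients β_vw, γ_hw and λ_hvw;
- w itself, entered twice (γ_w w and φ w).

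The variable w "is the continuous or binary characteristic along which we want to test heterogeneous impacts", and no centring or scaling is stated. The decision rule follows: "The test for heterogeneous treatment effects along" w is whether one can reject "\beta_{vw} = \beta_v, \gamma_{hw} = \gamma_h, \lambda_{hvw} = \lambda_{hv}) \forall (h, v". That is 3 + 3 + 9 = 15 restrictions, each setting an interaction equal to its main effect.

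The rule is the only general test given for the ten first-step dimensions, which include district, age, wealth, hospital distance and village size. Section 7.1 says that interactions with coloring variables will be estimated in the same way.

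**The concern.** Leaving the share terms aside, the effect of arm h at a given w in equation (4) is γ_h + γ_hw·w. It is constant in w only if γ_hw = 0. The stated null γ_hw = γ_h makes the effect γ_h(1 + w), which is double at w = 1. The same holds for β and λ.

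The rule therefore does not answer the section's own question. A real effect that is the same for everyone violates the null, and violates it more as the effect grows. One particular pattern of strong heterogeneity, exact doubling, satisfies it. The null also depends on coding. Swapping the reference category of a binary w reverses which group must have twice the effect. Changing a distance from kilometres to metres changes the null from γ_h(1 + w) to γ_h(1 + 1000w), with w in kilometres.

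At stake are the subgroup conclusions for the ten dimensions and any mechanism or intra-household reading that borrows the same test.

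**Working it through.** The plan gives no figure or significance level for this test, so there is nothing to reproduce. A two-sided 5% level is assumed throughout.

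**1. Closed form: one arm, balanced binary w.** Let V be the variance of the overall effect estimate and t its true value divided by √V. The values of t below are illustrative assumptions.

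- Each half-sample effect has variance 2V. So Var(γ_h) = 2V, Var(γ_hw) = 2V + 2V = 4V, and Cov = −2V.
- Var(γ_hw − γ_h) = 4V + 2V + 4V = 10V.
- With no heterogeneity, γ_hw − γ_h = −γ_h, so the non-centrality is t/√10: 0.885, 1.581 and 3.162 for t = 2.8, 5 and 10. False rejection is 0.144, 0.353 and 0.885.
- If the effect doubles, the overall effect is 1.5γ_h, so γ_hw = t√V/1.5 with standard error 2√V and non-centrality t/3. The test against zero has power 0.385 at t = 5 and 0.915 at t = 10. The stated test rejects 5%, because its null is true.

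**2. The plan's own enrollment figures (Section 5.4).** Arm A enrollment was 77.9% in Gulbarga and 78.8% in Mysore, with none in arm D. Take district as w (Gulbarga = 0) in a model with household arms only. Arm A has about 0.40 × 11,089 = 4,436 households. Assume an even district split, 2,218 each, and ignore clustering.

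- γ_A = 0.779 and γ_Aw = 0.788 − 0.779 = 0.009.
- Against zero: SE = √[(0.788×0.212 + 0.779×0.221)/2,218] = 0.0124, so z = 0.73.
- Stated restriction: 0.009 − 0.779 = −0.770, SE = √[(0.788×0.212 + 4×0.779×0.221)/2,218] = 0.0196, so |z| is about 39.

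With 30% to 70% of arm A in Gulbarga, |z| runs from about 32 to 41. A tenfold larger variance would still leave it above 10 (32/√10). This is the arm A restriction alone; enrollment in arms B and C does differ by district.

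**3. Simulation of the joint test.** From the plan: Table 1's allocation and 424 villages, here with 26 households each (11,024 in total, against 11,089 randomized). Assumed: residual SD 1, village SD 0.2, balanced binary w, zero spillovers and the same γ in arms A, B and C. A plain village cluster-robust variance stands in for HC2, and the duplicate w is dropped. There were 400 replicates, so the Monte Carlo SE near 5% is √(0.05×0.95/400) = 0.011.

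| True pattern | γ (SD) | Stated null, full eq. (4) | Zero null, full eq. (4) | Stated null, arms only | Zero null, arms only |
|---|---|---|---|---|---|
| No heterogeneity | 0 | 0.082 | 0.070 | 0.055 | 0.052 |
| No heterogeneity | 0.1 | 0.135 | 0.090 | 0.155 | 0.048 |
| No heterogeneity | 0.2 | 0.382 | 0.090 | 0.570 | 0.078 |
| No heterogeneity | 0.3 | 0.718 | 0.095 | 0.885 | 0.058 |
| Doubles at w = 1 | 0.1 | 0.045 | 0.258 | 0.045 | 0.365 |
| Doubles at w = 1 | 0.2 | 0.090 | 0.808 | 0.048 | 0.945 |
| Doubles at w = 1 | 0.3 | 0.075 | 0.992 | 0.050 | 1.000 |

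With a standard normal w, γ = 0.2 SD and no heterogeneity, the stated null is rejected 0.99 (full) and 1.00 (arms only). The zero null is rejected 0.095 and 0.048. The zero-null rates of 0.07 to 0.095 in the full model probably reflect a 15-degree-of-freedom chi-square test with the plain variance. They are a separate matter.

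**The case against.** The strongest reply is that this is a slip of notation. The section states its aim correctly, equation (4) is offered as an example, and Section 7.2 tests its spillover coefficients against zero. That may well be the explanation, but nothing in the plan restates this null as zero. The modifications promised after equation (4) are to mirror those in Section 7.1 (recoding village arms to shares, pooling arms A to C), and none of these alters the null. An equality null would be right if the main terms were multiplied by 1 − w with w binary. They are not, and w may be continuous.

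Some limits do stand:

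- False rejection needs at least one non-zero main or spillover coefficient. If all are zero, the two nulls coincide.
- Doubling is literal only for a one-unit difference in w from zero.
- The closed-form figures describe one restriction and a w that varies within villages. They do not describe the 15-restriction test, or village-level characteristics such as village size.
- The rule does not govern the main ITT and CATE estimates, the index adjustment in Section 7.4 or the machine-learning second step. The hypothesis on price sensitivity by predicted propensity has its own comparison.
- The duplicate w is editorial. Neither of its coefficients is in the tested null.

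**Conclusion.** The concern holds. As written, the test is wrong by algebra, whatever effect sizes are assumed. Its practical size depends on how large and how precisely estimated the true effects are. In the full equation with balanced binary w, a uniform effect of 0.1 to 0.3 SD is called heterogeneous 14% to 72% of the time, and a true doubling is flagged only 5% to 9% of the time. For a strong outcome such as enrollment, the arm A restriction rejects overwhelmingly although the two districts differ by 0.9 percentage points. These rates rest on the assumed 5% level, variance components and effect sizes listed above. The direction of the failure does not. Because the plan exists to fix the analysis before endline data are obtained, following the rule would mislead, and correcting it silently would be an undocumented departure. It must be fixed.

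**What to change.** Replace the decision rule in Section 7.3 with: *The test for heterogeneous effects along w_ij is the joint Wald test, using the village-level cluster-robust HC2 variance of Section 7.1, that β_vw = 0, γ_hw = 0 and λ_hvw = 0 for all h and v.* If only heterogeneity in household-level treatment is meant, limit the null to γ_hw = 0 and λ_hvw = 0, and say so. State the significance level. Delete either γ_w w_ij or φ w_ij from equation (4), since the two are perfectly collinear.

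The cost is one sentence and one deleted term, recorded in a dated amendment. No data collection or sample size is affected.
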